Levetiracetam Versus Valproate in Idiopathic Generalized Tonic-clonic Seizures

ID: NCT03940326

8.11.2020

Study protocol

This study was a non-randomized open label active-controlled clinical trial with a two-parallel-group design aimed to compare efficacy of levetiracetam (LEV) with valproate (VPA) for treatment of patients with idiopathic (genetic) generalized epilepsy. Patients aged ≥ 16 years with diagnosis of genetic generalized tonic-clonic seizures only (GTCS) or juvenile myoclonic epilepsy (JME) who were referred to our tertiary University hospital and epilepsy clinic were included. Normal brain magnetic resonance imaging (MRI), lack of focal epileptic discharges with or without generalized epileptiform discharges in electroencephalography (EEG) and seizure symptomatology in favor of GTCS or JME were mandatory. Patients with history of hepatic, renal and hematologic disorders, known psychosis, psychogenic non-epileptic seizure, status epilepticus and illegal drug abuse, patients who had been treated with LEV or VPA in the last 6 months and those with poor adherence to medications or plan for pregnancy were excluded. The study was approved by University ethics committee and performed in accordance with the International Conference on Harmonization Good Clinical Practice guidelines and the Declaration of Helsinki. All patients provided written informed consent before participation.

Patients were treated by LEV or VPA. LEV was started with 500 mg/day (twice daily as equal doses) and the dose was increases by 500 mg/week to a total dose of 2000 mg/day if needed. Starting dose for VPA was 500 mg/day with 500 mg/week increase to the maximum dose of 1500 mg/day in two divided doses based on clinician's decision. Patients, who experienced adverse events (AEs) during titration which could be ameliorated by dose reduction, were reverted to previous acceptable dose. If one episode of seizure occurred, doses were increased to maximum 3000 mg/ day for LEV and 2000 mg/day for VPA with the same titration protocol, according to clinician's judgment. Evaluations have scheduled at weeks 4, 12 and 26 after initiation of treatment. In each visit by neurologist, adherence to AED, seizure recurrence and AEs were assessed. The primary outcomes were time to first seizure and seizure freedom rate at 6 months after start of treatment. The secondary outcomes were defined as time to withdrawal and withdrawal rate at 6th month and also severity of adverse events. Withdrawal rate was calculated based on discontinuation of monotherapy with each medication due to AEs, lack of efficacy and need to drug switch or combination therapy.

Statistical analysis

SPSS version 19 software (SPSS Inc.) was used for statistical analysis. Chi-square test or Fisher's exact test were used to compare categorical variables between groups. Numerical variables were analyzed with student's t-test or Mann-Whitney test, according to distribution. Time to first seizure and time to withdrawal were analyzed using the Kaplan–Meier survival curves. For analysis of time to first seizure, patients who did not experience any seizure during the first 26 weeks of treatment were censored at the end of 26 weeks. For analysis of time to withdrawal, patients who discontinue medication before 26 weeks were considered to have the event. Cox's regression model was used to investigate time to withdrawal and time to first seizure. A Hazard ratio (HR) of less than 1 was considered in favor of LEV. P-value of less than 0.05 was considered statistically significant.

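### Two epilepsy syndromes are analysed together with no stratification and no syndrome-specific estimate, so the result cannot be read for GTCS-only patients

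*Combined protocol and SAP*

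**What the plan says.** The title is "Levetiracetam Versus Valproate in Idiopathic Generalized Tonic-clonic Seizures". The Study protocol section states a wider aim, to compare the drugs' efficacy "for treatment of patients with idiopathic (genetic) generalized epilepsy", and admits patients with "genetic generalized tonic-clonic seizures only (GTCS) or juvenile myoclonic epilepsy (JME". Seizure symptomatology pointing to one of these two syndromes is an entry requirement, so each patient's syndrome should be known at baseline. The design is a "non-randomized open label active-controlled clinical trial with a two-parallel-group design"; no balancing of the arms by syndrome is mentioned.

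On outcomes, the same section says: "The primary outcomes were time to first seizure and seizure freedom rate at 6 months after start of treatment". Time to withdrawal and withdrawal rate are secondary.

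Under Statistical analysis, "Cox's regression model was used to investigate time to withdrawal and time to first seizure", and "A Hazard ratio (HR) of less than 1 was considered in favor of LEV". Categorical variables are compared between groups by chi-square or Fisher's exact test. The Cox covariates are not listed. No stratum, subgroup or interaction by syndrome appears for any outcome.

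**The concern.** A single HR over two syndromes is an average, weighted towards the syndrome that supplies more events. If the levetiracetam (LEV) versus VPA effect were the same in both, little would be lost. If it differed, the average would dilute the effect in one syndrome or, in the extreme, offset opposite effects. Identical syndrome mix in the two arms does not prevent this, and the same holds for the pooled comparison of seizure freedom.

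What is at stake is how the result is read. A reader led by the title will apply it to GTCS-only patients, and the planned output gives no way to check whether it applies to them. There is a second, separate reason to bring syndrome into the model. Allocation was not randomized, so drug choice may have followed syndrome, and an unstratified HR would then mix a drug difference with a case-mix difference.

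**Working it through.** The documents give no sample size, event count, syndrome mix or expected effect, so there is no planned figure to reproduce. What follows is an illustration.

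**Inputs.** From the documents: 26-week follow-up with censoring at week 26. Assumed: exponential times; 26-week first-seizure risk on VPA of 25% in GTCS-only and 60% in JME; half of each syndrome on each drug; 30% or 50% JME.

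**Weekly hazards on VPA**, λ = −ln(1 − risk)/26:
- GTCS-only: 0.2877/26 = 0.0111
- JME: 0.9163/26 = 0.0352

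**26-week risks on LEV**, 1 − (1 − risk)^HR:
- GTCS-only, HR 0.7: 1 − 0.75^0.7 = 0.182 (VPA 0.25)
- JME, HR 1.4: 1 − 0.40^1.4 = 0.723 (VPA 0.60)

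**Overall risks at 30% JME:**
- LEV: 0.7 × 0.1824 + 0.3 × 0.7227 = 0.3445
- VPA: 0.7 × 0.25 + 0.3 × 0.60 = 0.3550

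**JME share of events at 30% JME:**
- VPA arm only: 0.18/0.355 = 51%
- Both arms: (0.2168 + 0.18)/(0.3445 + 0.3550) = 57%

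**Pooled HR.** The large-sample unstratified Cox estimate is exp(b), where b solves ∫[f₁ − f·e^b·S₁/(e^b·S₁ + S₀)]dt = 0 over 0 to 26 weeks. Here f₁ is the event density on LEV, f the total event density, and S₁ and S₀ the fractions still at risk on LEV and VPA. Solved numerically:

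| HR GTCS-only | HR JME | JME share of patients | Pooled HR |
|---|---|---|---|
| 0.7 | 1.4 | 30% | 0.97 |
| 0.7 | 1.4 | 50% | 1.10 |
| 0.7 | 1.0 | 30% | 0.84 |

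**Stratification alone.** In the first row, a Cox model stratified by syndrome with one common drug effect gives 1.04. It still does not reveal 0.7 and 1.4; only estimates within each syndrome do.

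**Confounding by syndrome.** Take a true HR of 1 in both syndromes, 40% JME, and 26-week risks of 50% (JME) and 30% (GTCS-only). If LEV goes to 60% of GTCS-only but 30% of JME patients, the unstratified HR is 0.82. With those two shares exchanged it is 1.22. The stratified HR is 1.00 in both cases.

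**Precision of the proposed analysis.** In the first row, events per patient are (0.3445 + 0.3550)/2 = 0.35, so an assumed 100 to 200 patients give about 35 to 70 events.
- 95% interval factor, exp(1.96 × √(4/d)), at 100 patients: JME, d = 19.8, about 2.4 either way; GTCS-only, d = 15.1, about 2.7.
- Interaction power for the twofold HR ratio at two-sided 0.05: about 17% (35 events) to 30% (70 events).
- Events for 80% power: 4 × (1.96 + 0.84)² × (1/0.57 + 1/0.43)/(ln 0.5)² ≈ 267.

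**The case against.** The strongest reply is that the pooled HR is the estimand the trial set itself. The aim names idiopathic generalized epilepsy, both enrolled syndromes belong to it, and averaging over related subtypes is common. That stands. A title narrower than the aim does not make the pooled analysis wrong.

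A reader might infer more: that the two drugs work differently or oppositely in the two syndromes, that the pooled result is therefore misleading, and that the plan lets one number decide which drug wins. The documents support none of this. Nothing in them suggests that the effect differs by syndrome. The sentence on an HR below 1 fixes the direction of the ratio; it is not a decision rule. Because the Cox covariates are not listed, syndrome may even have been adjusted for, although adjustment with one common drug effect would still give no syndrome-specific answer.

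It can also be said that the remedy would rarely settle the matter. That is largely right for a formal interaction test at plausible sizes. It is not a reason to withhold the syndrome-specific estimates: their wide intervals would show how little the trial says about each syndrome separately, which the pooled HR does not show.

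**Conclusion.** The point holds as a gap in stratification and reporting, not as an error in the pooled estimate. As described, the analysis can answer for the enrolled mix but not for GTCS-only patients, and in a non-randomized comparison it leaves syndrome as an unaddressed potential confounder.

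The size is unknown. Under the stated assumptions, an HR of 0.7 in GTCS-only appears as a pooled 0.84 if JME has no effect, and as 0.97 or 1.10 (30% or 50% JME) if JME has an HR of 1.4. The change of direction between the last two comes from the assumed reversal of effect and is not a prediction for this trial.

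**What to change.** 1. Stratify each Cox model (time to first seizure and time to withdrawal) by syndrome. This removes confounding by syndrome, but not by other factors that guided drug choice.
2. Beside the pooled value, report the LEV versus VPA HR and 26-week seizure freedom within GTCS-only and within JME, each with a 95% confidence interval and the numbers of patients and events by arm.
3. Label any drug-by-syndrome term as exploratory, and do not read a non-significant one as evidence of equal effects.
4. Describe the pooled HR as an average over the enrolled mix, state that mix, and rest any statement about GTCS-only patients on the GTCS-only stratum.

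The cost is some analysis-plan wording and one extra table, using a variable the trial already needs for eligibility. The downside is wide intervals and low interaction power. The plan is written in the past tense; if the data have already been analysed, these results should be labelled as additional analyses. This is a cheap improvement.

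### Drug allocation is non-randomised with no stated rule, yet no adjustment for baseline factors is stated; LEV or VPA use that ended more than 6 months ago is one potential confounder among several

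*Combined protocol and SAP*

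**What the plan says.** The Study protocol section describes a "non-randomized open label active-controlled clinical trial" that enrols two syndromes ("genetic generalized tonic-clonic seizures only (GTCS) or juvenile myoclonic epilepsy (JME"). On past use of the compared drugs, the only exclusion is of "patients who had been treated with LEV or VPA in the last 6 months". Patients need not be newly diagnosed or previously untreated, and they come from referrals to a tertiary centre. Poor adherence is a separate exclusion.

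On allocation, the treatment paragraph says only "Patients were treated by LEV or VPA"; it gives no rule and no ratio. The primary outcomes are time to first seizure and the proportion seizure-free at 6 months. Withdrawal, a secondary outcome, counts "discontinuation of monotherapy with each medication due to AEs, lack of efficacy" and the need to switch or combine drugs.

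Under Statistical analysis, chi-square or Fisher's "exact test were used to compare categorical variables between groups", and Cox's "regression model was used to investigate time to withdrawal and time to first seizure". No covariate, stratification, matching or weighting is named. A hazard ratio (HR) below 1 favours LEV, and significance is set at 0.05. No sample size or expected event rate is given.

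**The concern.** Without randomisation, whoever chooses the drug can use what is known about the patient. Any baseline factor that influences that choice and also predicts seizures or withdrawal will distort the comparison between arms. A chi-square or Fisher test cannot correct for this, and a Cox model does so only through the covariates put into it.

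The eligibility text leaves room for one specific factor of this kind. A patient who stopped VPA a year ago meets the 6-month rule, and that history is an obvious reason to give LEV now; the same holds with the drugs reversed. The reason for stopping matters. Past inefficacy may mark epilepsy that is harder to control, and so bear on both primary outcomes. Past intolerance need not change seizure risk but may bear on withdrawal. Past VPA stoppers given LEV would load the LEV arm, past LEV stoppers given VPA would load the VPA arm, and the two can cancel. A reader of an unadjusted result could not tell how much of a difference reflects the patients rather than the drugs. The same applies to syndrome (GTCS-only or JME), which is certain to vary among the patients eligible for this trial.

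**Working it through.** The documents contain no figure to reproduce on this point. What follows is illustration, and every input is an assumption.

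**Inputs.** No true drug difference; 60% of other patients seizure-free at 26 weeks; 15% of all patients once stopped a study drug; arms of equal size; constant hazards. Half of the stoppers stopped for inefficacy (seizure hazard doubled) and half for intolerance (seizure hazard unchanged). In the base case every stopper now receives the other drug.

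**Formula.** Doubling the hazard turns 0.60 into 0.60² = 0.36. If a fraction q of an arm are inefficacy stoppers, the seizure-free proportion is

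S = 0.60(1 − q) + 0.36q = 0.60 − 0.24q,

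and the apparent HR (LEV to VPA) is close to ln S_LEV / ln S_VPA. Numerical integration of the large-sample Cox estimate gives the HRs in the table.

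**Example.** If all 15% stopped VPA and moved to LEV, they form 30% of the LEV arm, so q = 0.15 there and 0 in the VPA arm. Then S_LEV = 0.60 − 0.036 = 0.564 and S_VPA = 0.60. The ratio is 0.573/0.511 = 1.12.

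| Stopped VPA / LEV (% of all patients) | q LEV / q VPA | Seizure-free LEV / VPA | HR |
|---|---|---|---|
| 15 / 0 | 0.15 / 0 | 56.4% / 60.0% | 1.12 |
| 10 / 5 | 0.10 / 0.05 | 57.6% / 58.8% | 1.04 |
| 7.5 / 7.5 | 0.075 / 0.075 | 58.2% / 58.2% | 1.00 |
| 5 / 10 | 0.05 / 0.10 | 58.8% / 57.6% | 0.96 |
| 0 / 15 | 0 / 0.15 | 60.0% / 56.4% | 0.89 |

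**Varying the assumptions.**
- If all stopped for inefficacy, the range is 1.25 to 0.80. If all stopped for intolerance, it is 1.00 throughout.
- If 75% rather than all receive the other drug, the range is 1.06 to 0.94. At 50% there is no channelling and the HR is 1.00.
- If a third stopped for a neutral reason and the rest split equally, the one-sided q is 0.10, S_LEV is 0.576 and the HR is 1.08. For the 10/5 split it is 1.03.
- If past exposure marks lower risk (hazard multiplied by 0.67), the sign reverses: 30% exposed in the LEV arm against 10% in the VPA arm gives 0.93.
- With 5% to 20% past stoppers, an inefficacy hazard ratio of 1.5 to 3, an inefficacy share of 25% to 75% and full switching, the HR lies between 0.70 and 1.43.

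**False positives.** Simulation with an assumed 50 per arm and 4,000 replicates, full switching:

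| Scenario | Chi-square | Cox |
|---|---|---|
| 15/0, half inefficacy | 6.9% | 6.2% |
| 15/0, all inefficacy | 11.7% | 10.6% |
| 10/5, half inefficacy | 5.2% | 4.7% |
| 7.5/7.5, half inefficacy | 5.1% | 4.6% |

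Monte Carlo error is 0.3 to 0.5 percentage points.

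**Withdrawal.** With 20% withdrawing otherwise, full switching and half stopping for each reason, the HR runs from 1.28 to 0.78 if either reason doubles the withdrawal hazard. It runs from 1.14 to 0.88 if only one does.

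**The case against.** The strongest objection is that bias from past exposure needs several things at once: such patients enrolled, stopped mostly for inefficacy, mostly on one drug, and mostly received the other. The documents show none of these. With a 10/5 or an equal split and half stopping for inefficacy, the false-positive rate stays near 5%. This stands, and it limits how much weight past exposure alone can carry.

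Past exposure is also only a fragment of the real gap, which is the absence of stated adjustment for any baseline factor. That stands too, and it is why the fix centres on a general adjusted analysis.

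A two-way split into inefficacy and intolerance leaves out patients who stopped for other reasons, such as remission or access. The plan's own separation of reasons defines withdrawal on study, not past history. Counting neutral reasons lowers the HRs, as shown above. At 50 per arm, 15% is 15 of 100 patients, so each of two reasons would hold only 7 or 8, and separate model terms would be fragile. The poor-adherence exclusion may also remove some past stoppers. All of this stands.

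Finally, the text is a short summary, and silence is not absence. The sentence on categorical variables could cover baseline drug history. A reader might infer that the Cox models had no covariates, but the documents show only that none is stated.

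**Conclusion.** The concern holds as a gap in the stated analysis. Allocation is non-randomised without a rule, and no adjustment is stated, so baseline differences can bias both primary outcomes. Past LEV or VPA use is one potential contributor of unknown presence, size and direction. That such patients are eligible is inferred from the exclusion wording; no sentence admits them expressly.

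On assumed inputs the bias ranges from nil to moderate. It matters mainly if past stopping was for inefficacy, concentrated on one drug and followed by a switch.

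Two stronger readings are tempting. A reader might infer that the result is confounded by this history, or that one drug is favoured. The documents give no counts, no reasons for stopping and no allocation pattern, so they support neither. A reader might also take the 12% false-positive figure as expected. It requires 15% past stoppers, all for inefficacy, all on one drug and all switched.

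The change should be made, with medium confidence. It is cheap, and without it readers cannot judge how far the arms are comparable.

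**What to change.** Make the main comparison an adjusted one:
- Use Cox models for time to first seizure and time to withdrawal, and a logistic or stratified analysis for 6-month seizure freedom. State every covariate.
- Adjust for syndrome (GTCS-only or JME), other recorded baseline prognostic factors, and a single term for LEV or VPA use before the 6-month window. Split that term by reason only if numbers allow.
- Report past exposure by arm, with which drug was stopped and why (inefficacy, intolerance, other), from chart review if it was not recorded.
- Add a sensitivity analysis in patients never exposed to either drug. This is the fallback if the exposure term cannot be estimated.
- State that residual confounding from non-random allocation remains.

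The cost is some chart review and a modest loss of precision. The figures below assume 50 per arm and come from a model with separate inefficacy and intolerance terms; a single term was not run.
- **10/5 split, half inefficacy:** adjustment raises the standard error of the log HR from 0.313 to 0.322 (0.322/0.313 = 1.03, about 3%), and of the log odds ratio from 0.410 to 0.426 (about 4%). The never-exposed analysis gives 0.350 (12%) and 0.451 (10%).
- **Fully one-sided loading with full switching:** exposed patients sit in one arm only, so adjustment costs the same as restriction. The standard error of the log HR rises from 0.314 to 0.356 (13%), or from 0.308 to 0.356 (16%) if all stopped for inefficacy.

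These simulations contain no other confounder, so they do not show that the adjusted estimate would be unbiased in this trial.

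### Patients taking, or just off, another antiepileptic drug may enter, and nothing in the plan protects the primary comparison if they are unevenly split between the arms

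*Combined protocol and SAP*

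**What the plan says.** All references are to the combined protocol and SAP.

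- **Design and source of patients (Study protocol).** The trial is a "non-randomized open label active-controlled clinical trial with a two-parallel-group design". Patients with the eligible diagnoses "who were referred to our tertiary University hospital and epilepsy clinic were included". Entry is not limited to newly diagnosed or untreated patients.
- **Prior drugs (Study protocol, exclusions).** The exclusion list ends with "patients who had been treated with LEV or VPA in the last 6 months and those with poor adherence to medications or plan for pregnancy". No other antiepileptic drug is named.
- **Treatment (Study protocol).** "Patients were treated by LEV or VPA". Starting doses and titration follow, but nothing says whether an earlier drug is stopped, tapered or kept.
- **Outcomes (Study protocol).** "The primary outcomes were time to first seizure and seizure freedom rate at 6 months after start of treatment". The secondary withdrawal outcome is defined as follows: "Withdrawal rate was calculated based on discontinuation of monotherapy with each medication due to AEs, lack of efficacy and need to drug switch or combination", meaning treatment with a further drug.
- **Analysis (Statistical analysis).** Kaplan–Meier curves and Cox regression are used for both time-to-event outcomes, and chi-square or Fisher tests for categorical ones. No covariate is named, and no early period is left out of the 26 weeks.

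**The concern.** The clock for both primary outcomes starts with the study drug. A patient whose earlier drug was stopped around that time may have seizures because of the stopping, and they count against LEV or VPA. A patient whose earlier drug is still present may be protected by it, and the protection counts in favor of LEV or VPA. The eligibility text allows both situations, and the analysis cannot separate them from the effect of the study drug.

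In a randomized trial, such patients would be balanced between arms on average. Here allocation is neither randomized nor described by any rule, so the clinician's choice of drug could depend on what the patient was already taking. If it did, a difference in prior-drug status would appear as a difference between LEV and VPA.

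**Working it through.** **Step 1. Look for a rule that closes the gap.** Five kinds of rule would do so: an exclusion for other antiepileptic drugs, a restriction to untreated patients, a washout or run-in, a concomitant-drug rule, or adjustment for prior drug. None is in the document. The tertiary referral source, the 6-month window and the exclusion for poor adherence are all consistent with already-treated patients being eligible, but do not prove that any entered. The monotherapy wording in the withdrawal definition suggests that an earlier drug was not meant to continue, but not when or how it ended.

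**Step 2. Size of a possible bias.** The plan gives no sample size, event rate or effect size, so there is no figure of its own to reproduce. The inputs below are assumptions, used only for illustration:

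- no true LEV–VPA difference;
- S0, 26-week seizure freedom in unaffected patients: 50% or 70%;
- m, the hazard multiplier in affected patients over the 26 weeks: 2 (seizures after stopping a drug), 3 (a stronger version) or 0.5 (protective carry-over);
- s, the share of affected patients in an arm.

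Seizure freedom in an arm is S = (1 − s) × S0 + s × S0^m. The cumulative hazard ratio at 26 weeks is ln(S_LEV) / ln(S_VPA), which stands in for the Cox hazard ratio. Below 1 favors LEV, as in the plan.

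Worked case (S0 = 0.50, m = 2, 10% of LEV and 30% of VPA affected):

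- S_LEV = 0.9 × 0.50 + 0.1 × 0.25 = 0.475
- S_VPA = 0.7 × 0.50 + 0.3 × 0.25 = 0.425
- ratio = ln(0.475) / ln(0.425) = 0.870

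| m | LEV share | VPA share | S0 = 50%: LEV vs VPA, ratio | S0 = 70%: LEV vs VPA, ratio |
|---|---|---|---|---|
| 2 | 10% | 30% | 47.5% vs 42.5%, 0.870 | 67.9% vs 63.7%, 0.858 |
| 2 | 30% | 10% | 42.5% vs 47.5%, 1.149 | 63.7% vs 67.9%, 1.165 |
| 0.5 | 10% | 30% | 52.1% vs 56.2%, 1.133 | 71.4% vs 74.1%, 1.125 |
| 3 | 0% | 40% | 50.0% vs 35.0%, 0.660 | 70.0% vs 55.7%, 0.610 |
| 2 | 20% | 20% | 45.0% vs 45.0%, 1.000 | 65.8% vs 65.8%, 1.000 |

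The bias can go either way, depending on which arm holds more affected patients and whether the earlier drug harms by its withdrawal or protects by its presence.

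**Step 3. Equal shares with a true difference.** Assume seizure freedom of 70% on LEV and 60% on VPA in unaffected patients, with 20% affected at doubled hazard in each arm.

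- Without affected patients: ln(0.70) / ln(0.60) = 0.698
- With them: S_LEV = 0.8 × 0.70 + 0.2 × 0.49 = 0.658; S_VPA = 0.8 × 0.60 + 0.2 × 0.36 = 0.552; ratio = 0.704
- If stopping a drug instead multiplies seizure freedom by 0.7 in affected patients: S_LEV = 0.658; S_VPA = 0.8 × 0.60 + 0.2 × 0.42 = 0.564; ratio = 0.731

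Equal shares therefore move the contrast little, while seizure freedom itself falls in both arms.

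**The case against.** The strongest objection is that contamination is permitted, not shown. Tertiary referral does not establish prior treatment, and the share of affected patients could be zero. This stands, and it limits the point to an unprotected comparison.

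The monotherapy wording may also mean that earlier drugs were stopped. That makes long-term continuation less likely but leaves the transition open, and the transition falls just after time zero.

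A reader might infer more than the text supports in four ways:

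- **That a converting patient is a combination-therapy failure from day 0.** The withdrawal definition counts stopping monotherapy because combination became necessary, and the analysis section counts discontinuing medication before 26 weeks. A patient who starts LEV or VPA while an earlier drug is tapered has done neither.
- **That the contrast is seriously diluted even with equal shares.** In the cases in step 3 the ratio moves from 0.698 to 0.704 or 0.731, which is modest.
- **That the share of follow-up affected measures the harm.** An assumed overlap of 4 to 8 weeks is 4/26 = 15% to 8/26 = 31% of the period, but the overlap has no source in the documents and the percentage says nothing about bias in a hazard ratio.
- **That the primary population should be cut to patients on no other drug at the first dose.** This would keep someone who stopped a drug the day before. Since the document is written in the past tense, it might also redefine the primary population after outcomes are known.

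Finally, this could be called one part of a wider lack of baseline adjustment. That is fair, but prior-drug status is a specific factor that the eligibility text leaves open and the outcome definition assumes away.

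**Conclusion.** The point holds as a gap that could bias the result, not as evidence that it did. Eligibility admits patients taking or just off another antiepileptic drug, the outcome definition presumes monotherapy, and neither design nor model guards against an uneven split.

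With no true difference, a doubled hazard and a 10% against 30% split, the spurious hazard ratio is about 0.86 to 0.87 or 1.15 to 1.17, a difference of 4 to 5 percentage points in seizure freedom. The more extreme 0% against 40% split with a tripled hazard gives 0.61 to 0.66. All these values rest on assumed shares, hazard multipliers and baseline seizure freedom. The mixture also applies the multiplier over the whole 26 weeks, whereas a real transition effect would probably be concentrated early. Equal shares leave the ratio close to its true value and mainly shift the within-arm rates. This is a cheap improvement.

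**What to change.** 1. Record for every patient each antiepileptic drug in use at the first dose of study drug, and the date of the last dose of any earlier one. The date matters because status on the day of entry misses patients who have just stopped.
2. Report prior-drug status by arm in the baseline table.
3. Include prior-drug status as a covariate in the Cox models.
4. Repeat both primary outcomes excluding patients with a current or recently stopped other antiepileptic drug. This matters most for the seizure-freedom rate, since the chi-square or Fisher comparison takes no covariate. Define "recently stopped" before outcomes are examined by arm. Leave the primary population as it is.
5. State how prior and concurrent antiepileptic drugs were handled, so that the eligibility text and the monotherapy outcome definition are reconciled. No washout or conversion rule is proposed here; that is a clinical matter.

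The cost is a little more data extraction, one covariate, one sensitivity analysis and a short statement. The sensitivity analysis will have fewer patients and wider intervals if any are excluded. If drug history was not recorded at entry and cannot be recovered, that should be reported as a limitation.

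### Non-randomized comparison with no stated allocation rule and no confounder control specified, so a prognostic imbalance between arms would be read as a drug effect

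*Combined protocol and SAP*

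**What the plan says.** Under Study protocol, the trial is a "non-randomized open label active-controlled clinical trial with a two-parallel-group design" that sets out to compare the efficacy of levetiracetam (LEV) with that of valproate (VPA). On who received which drug it says only that "Patients were treated by LEV or VPA". The references there to the clinician's discretion concern dose, not choice of drug.

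Eligibility admits two syndromes (GTCS only, or JME) and patients both with and without generalized discharges on EEG, so at least these two characteristics vary within the study population.

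On outcomes: "The primary outcomes were time to first seizure and seizure freedom rate at 6 months after start of treatment". Time to withdrawal and the 6-month withdrawal rate are secondary.

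Under Statistical analysis, chi-square or Fisher's "exact test were used to compare categorical variables between groups". Kaplan–Meier curves are used for the time-to-event outcomes, and Cox's "regression model was used to investigate time to withdrawal and time to first seizure". A hazard ratio (HR) below 1 is read as favouring LEV. No covariate, stratification, matching, weighting, propensity score or sensitivity analysis for confounding is mentioned.

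**The concern.** Without randomization, nothing in the design makes the two arms alike in expectation. Whatever led a patient to one drug rather than the other may also predict seizures or withdrawal. An unadjusted comparison then adds the prognostic difference to the drug effect, yet the plan reads the result directly as evidence for one drug. It can show a difference between equally effective drugs or hide a real one. A larger sample does not help: the bias stays the same size while the standard error shrinks, so false positives become more frequent. Both primary outcomes and both withdrawal outcomes are exposed. Imbalance in a factor unrelated to outcome does no harm.

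**Working it through.** **What the text settles.** There is no planned figure to reproduce: the documents give no sample size, event rate, effect size, allocation ratio or power. The point rests on the text.

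- 6-month seizure freedom and withdrawal rates: the only method named for categorical data is an unadjusted test.
- Time to first seizure and time to withdrawal: the Kaplan–Meier curves are crude. The Cox model is named without saying whether it is univariable or multivariable, so here the defect is that adjustment is not specified.

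**Illustration of size (all inputs assumed).** The drugs are equally effective. One binary factor multiplies the seizure hazard by *h*. Its prevalence is p₁ in one arm and p₀ in the other. Seizure times are exponential, censored at 26 weeks, with 50% having a seizure by then. Tests are two-sided at 5% (the plan gives 0.05 without sidedness).

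Initial crude HR = (p₁h + 1 − p₁)/(p₀h + 1 − p₀).

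26-week seizure freedom in an arm = p·s₁ + (1 − p)·s₀, with s₁ = s₀^h and s₀ + s₁ = 1, so that overall risk is 50%.

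Worked case, 60% vs 40% with h = 2:

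- s₀ = 0.618 and s₁ = 0.382.
- Seizure freedom is 0.6 × 0.382 + 0.4 × 0.618 = 0.4764 in one arm and 0.4 × 0.382 + 0.6 × 0.618 = 0.5236 in the other.
- The risks are 52.4% and 47.6%, a spurious difference of 4.7 points.
- For the two-proportion test at 100 per arm, the null SE is √(2 × 0.25/100) = 0.0707 and the SE under the difference is 0.0706. The rejection rate is Φ((0.0472 − 1.96 × 0.0707)/0.0706) + Φ((−0.0472 − 1.96 × 0.0707)/0.0706) = 0.098 + 0.004, about 10%.

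The last column below is simulated with the crude log-rank test (4,000 trials per scenario, Monte Carlo SE about 0.3 points at 5%). Risk differences are taken before rounding.

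| Prevalence | h | Initial crude HR | 26-week risk (%) | Difference (points) | False positives (%) at 50/100/200 per arm |
|---|---|---|---|---|---|
| 55 vs 45 | 1.5 | 1.275/1.225 = 1.04 | 50.7 vs 49.3 | 1.4 | 4.2/5.9/6.3 |
| 55 vs 45 | 2 | 1.55/1.45 = 1.07 | 51.2 vs 48.8 | 2.4 | 6.0/6.8/8.2 |
| 60 vs 40 | 2 | 1.6/1.4 = 1.14 | 52.4 vs 47.6 | 4.7 | 7.6/10/16 |
| 70 vs 30 | 2 | 1.7/1.3 = 1.31 | 54.7 vs 45.3 | 9.4 | 17/27/50 |
| 70 vs 30 | 3 | 2.4/1.6 = 1.50 | 57.3 vs 42.7 | 14.6 | 31/55/83 |

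With a 50/50 split, rejection is 5.3/5.2/4.8%, as it should be. Chi-square on the 6-month rate agrees with the log-rank within about 2 points. With 30% or 70% events (50 and 200 per arm), the first row gives 5.3–6.5%, 60 vs 40 with h = 2 gives 6.4–21%, and the last row 20–94%.

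**Direct check with Cox regression.** The factor is present in 30% of LEV and 60% of VPA patients, 26-week seizure freedom is 75% without it, and there are 1,000 trials per setting at 50 and 100 per arm.

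- h = 2: a treatment-only Cox model gives a median drug HR of about 0.82 and rejects in 8.1% and 14.6%. Adding the factor gives HRs of 1.01 and 1.02 and rejection of 5.4% and 5.7%.
- h = 3: treatment only gives about 0.73, with 16.2% and 27.6%. Adjusted, the HRs are 1.01 and 1.00, with 5.0% and 5.2%.

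**Limit of adjustment.** With two independent factors, each 60 vs 40 with h = 2, crude false positives are 16/25/47% at 50/100/200 per arm. Stratifying on one leaves 7.4/10/16%. Stratifying on both gives 4.3/5.4/5.2%. Adjustment removes only the part due to factors that are measured.

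**The case against.** Several points on the other side are fair.

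- **The Cox model can carry covariates, and silence does not prove that it was univariable.** This stands, and it limits the claim for the two time-to-event outcomes to adjustment not being specified. It does not remove the problem: an unspecified covariate set cannot be interpreted and leaves the choice open after results are seen.
- **The chi-square sentence may describe baseline tables.** It sits beside "Numerical variables were analyzed with student's t-test or Mann-Whitney test, according to distribution", and no listed outcome is clearly numerical apart from the times, which have their own methods. The ambiguity is real. But if the sentence covers baseline only, a co-primary outcome has no method at all. Testing baseline differences is not confounder control, and no rule is given for acting on them.
- **Eligibility restriction is a partial form of control.** It narrows both arms alike, but it does not balance the characteristics left free, including syndrome and EEG status.
- **The magnitudes are assumed and run from negligible to extreme.** This stands. The documents do not show that any imbalance occurred, or that syndrome or EEG status predicts outcome. The simulations therefore cannot carry the severity rating, which rests on the non-randomized design and the absence of any specified control.
- **The log-rank test is not named in the plan.** True, but the direct Cox check shows the same behaviour.
- **The document is written in the past tense, so covariates may no longer be fixable before results are seen.** This affects how the adjusted analysis is labelled, not whether it is needed.

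**Conclusion.** The concern holds and must be fixed. A non-randomized efficacy comparison has no stated allocation rule, only unadjusted tests for the 6-month rates, and a Cox model with no covariates specified. As written, neither a difference between the drugs nor its absence can be attributed to the drugs. Confidence in the omission is high. The size and direction of any bias in this trial cannot be obtained from the documents. In the illustration, a mild imbalance in a weak factor leaves the error rate near 5%, a moderate one (60 vs 40, hazard doubled) raises it to 7.6–16%, and strong ones go well beyond. All of these depend on assumed prevalence, factor strength, event rate and arm size.

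**What to change.** 1. State how patients came to receive LEV or VPA, and report baseline balance by arm.
2. Compare time to first seizure, and time to withdrawal, with a Cox model containing treatment, syndrome (GTCS only vs JME), generalized EEG discharges (yes/no), age and sex. Add pre-treatment seizure frequency and prior antiepileptic drug use where recorded.
3. For the 6-month seizure-freedom and withdrawal rates only, replace chi-square/Fisher with an adjusted risk difference and 95% confidence interval on the same covariates. Logistic regression with standardization or inverse-probability weighting would serve equally well. If events are few, use one propensity score instead of the full list.
4. Fix the covariates without reference to outcome results. If outcomes have already been seen, label the adjusted analyses post hoc.
5. State that unmeasured confounding remains, so that adjustment reduces the bias but does not remove it.

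The cost is SAP wording and a modest amount of extra analysis. Syndrome and EEG status are established at eligibility, and age is checked there. The documents do not show that seizure frequency or wider drug history was collected; they mention only LEV or VPA use in the last 6 months, as an exclusion. Intervals may be slightly wider.
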